APPENDIX A: Schedule of Treatment and Evaluations

	Screening -21 Days	Cycle 1	All Other Cycles	Every 6 Weeks ± 5 Days from Cycle 1-Day 1	End of Study or Early Termination	Follow- up ¹²
Signed Informed Consent	X					
Review Inclusion/Exclusion		X				
Medical History ¹	X					
Physical Examination	X	X	X		X	
Height (cm)	X					
Weight (kg)	X	X	X			
BSA Calculation ²		X	X			
Vital Signs ³	X	X	X		X	
Karnofsky Performance Status	X	X	X		X	
MRI scan / Tumor Assessments	X ⁴			X ⁸	X ^{8,13}	
ECG	X	X ¹⁵	X ¹⁵		X ¹³	
ECHO (with ejection fraction)	X		X ¹¹		X ¹¹	
CBC w/differential & platelets ⁵	X	X ¹⁴	X		X	
Serum Chemistries ^{5,6}	X	X ¹⁴	X		X	
Urinalysis ⁷	X				X	
Serum/Urine Pregnancy Test	X					
ALDOXORUBICIN Administration		X	X			
Concomitant Medications ⁹	X	X	X		X	
Adverse Events ¹⁰		X	X		X	
Telephone Follow-Up						X

NOTE: All assessments must be performed within 72 hours of each specified time parameter, except Cycle 1 (see Section 6 for details).

CLINICAL PROTOCOL

TITLE: An Open-Label Pilot Phase 2 Study to Investigate the Preliminary Efficacy and Safety of Aldoxorubicin in Subjects with Unresectable Glioblastoma Whose Tumors Have Progressed Following Prior Treatment with Surgery, Radiation and Temozolomide

PROTOCOL NUMBER: ALDOXORUBICIN-P2-GBM-01

STUDY DRUG: Aldoxorubicin

IND NUMBER: 119437

SPONSOR: CytRx Corporation
[name]
[name]
[contact]
[contact]

SAFETY [contact]

SAFETY [contact]

ORIGINAL PROTOCOL: August 9, 2013

AMENDMENT 1: November 12, 2013

AMENDMENT 2: February 4, 2014

AMENDMENT 3: September 10, 2014

CONFIDENTIAL

The information contained in this document is confidential and the proprietary property of CytRx Corporation. Any unauthorized use or disclosure of such information without the prior written authorization of CytRx Corporation is prohibited.

SYNOPSIS

Name of Sponsor/Company: CytRx Corporation	
Protocol Number: ALDOXORUBICIN-P2-GBM-01	Phase of Development: 2
Title of the Protocol: An Open-Label Pilot Phase 2 Study to Investigate the Preliminary Efficacy and Safety of Aldoxorubicin in Subjects with Unresectable Glioblastoma Whose Tumors Have Progressed Following Prior Treatment with Surgery, Radiation and Temozolomide	
Primary Objectives: The primary objective of this study is to determine the preliminary efficacy of administration of ALDOXORUBICIN to subjects with unresectable glioblastoma (GBM) whose tumors have progressed following prior treatment with surgery, radiation and temozolomide, as measured by PFS according to the Response Assessment in Neuro-Oncology (RANO) Working Group Criteria (see Appendix F) and OS.	
Secondary Objectives: The secondary objectives of this study are to evaluate the safety of ALDOXORUBICIN in this population assessed by the frequency and severity of adverse events (AEs), abnormal findings on physical examination, laboratory tests, vital signs, echocardiogram (ECHO) evaluations, electrocardiogram (ECG) results, weight, and the change in performance status as measured by the Karnofsky Performance Scale.	
Study Rationale and Significance: ALDOXORUBICIN is a novel prodrug that binds covalently to albumin in the circulation. The drug is accumulated in tumors and doxorubicin is released in the tumor by cleaving the acid labile linker (EMCH) in the low pH tumor environment. This carrier-linked prodrug has demonstrated enhanced anti-tumor activity with reduced toxicity in several murine models when compared with free doxorubicin. Patients with unresectable GBM who have failed prior surgery, radiation and chemotherapy with temozolomide regimens and bevacizumab have an extremely poor prognosis with progression-free survival (PFS) of around 8 weeks and median overall survival (OS) of approximately 8-16 weeks, depending on whether salvage therapy is administered. Recently, we have demonstrated in an orthotopic xenograft model of GBM in mice that ALDOXORUBICIN significantly retards the growth of the tumor and doubles the survival of animals when compared to treatment with either saline or doxorubicin. We have also shown that this molecule collects inside the tumor and not in normal brain parenchyma. Doxorubicin does not penetrate into either the tumor or the brain. Thus, ALDOXORUBICIN may be able to effectively treat patients with advanced GBM that have progressed after standard therapies.	

Name of Sponsor/Company: CytRx Corporation	
Protocol Number: ALDOXORUBICIN-P2-GBM-01	Phase of Development: 2
Study Design and Methodology: This is a phase 2 open-label, pilot study evaluating the preliminary efficacy and safety of ALDOXORUBICIN administered at either 350 mg/m ² (260 mg/m ² doxorubicin equivalent) or 250 mg/m ² (185 mg/m ² doxorubicin equivalent) intravenously on Day 1, every 21 days until evidence of tumor progression, unacceptable toxicity or withdrawal of consent. Subjects will be randomly assigned to either dose of ALDOXORUBICIN. G-CSF (Neupogen or Neulasta) should be administered as primary prophylaxis to all subjects according to the ASCO Guidelines (see Appendix E). Tumor response (complete response [CR], partial response [PR] and stable disease [SD]) will be monitored at Screening, then every 6 weeks ± 5 days using the RANO Working Group Criteria (see Appendix F), and treatment will continue every 21 days until tumor progression is observed, unacceptable toxicity occurs, or consent is withdrawn. Median PFS, PFS at 12 and 18 weeks, and 6 months, SD rate at 12 weeks, and OS will be monitored as other primary objectives. Subjects will visit the study site every 21 days for their IV infusions, at which time safety monitoring, including AEs, a directed physical examination, laboratory evaluations (serum chemistry, complete blood count [CBC], and urinalysis), vital signs, weight measurements, Karnofsky Performance Status (see Appendix B), documentation of corticosteroid usage and ECGs will be performed. Cardiac function will also be followed periodically using ECHOs.	

Name of Sponsor/Company: CytRx Corporation	
Protocol Number: ALDOXORUBICIN-P2-GBM-01	Phase of Development: 2
Study Population and Main Criteria for Inclusion/Exclusion:	
Inclusion Criteria:	
Subjects must meet the following criteria to be included in the study:	

 1. Age \geq18 years of age; male or female. 2. Histologically or cytologically confirmed unresectable GBM. Subjects with recurrent disease whose prior pathology demonstrated GBM will not need to be re-biopsied. Subjects with prior low-grade glioma or anaplastic glioma are eligible if histological assessment demonstrates transformation into GBM. 3. Cancer progression after treatment with the following: surgery, radiation therapy and temozolomide with no other therapy prior to tumor recurrence. 
 a. Radiographic progression by RANO Working Group Criteria (see Appendix F) will be confirmed by Imaging Endpoints, a central imaging vendor; or b. Confirmation by tumor biopsy if conducted within 4 weeks of Randomization. 4. An interval of at least 12 weeks after last dose of radiation and temozolomide is required, unless cancer progression is proven by diagnostic tumor biopsy. If temozolomide is being used in a maintenance phase, there must be a 28-day washout period prior to Randomization. 5. Stable or decreasing dose of corticosteroids for at least 7 days prior to Randomization. 6. Capable of providing informed consent and complying with trial procedures. 7. Karnofsky Performance Status (see Appendix B) \geq70. 8. Life expectancy \geq8 weeks. 9. Measurable tumor lesions according to RANO Working Group Criteria (see Appendix F). 
 a. In the case that there is "non-measurable" disease due to a radical surgical resection prior to screening, the subject may still qualify if Inclusion #3(b) is met. 10. Women must not be able to become pregnant (e.g. post-menopausal for at least 1 year, surgically sterile, or practicing adequate birth control methods) for the duration of the study. (Adequate contraception includes: oral contraception, implanted contraception, intrauterine device implanted for at least 3 months, or barrier method in conjunction with spermicide.) 11. Women of child bearing potential must have a negative serum or urine pregnancy test at the Screening Visit and be non-lactating. 12. Geographic accessibility to the site, i.e. the ability to come to the study site for each scheduled appointment and evaluation. 	
Exclusion Criteria:	
Subjects meeting the following criteria will not be enrolled:	

 1. Prior exposure to an anthracycline. 2. Any therapeutic regimen for treatment of recurrent tumor after first line treatment with surgery, radiation and temozolomide. 3. Prior treatment with bevacizumab or an experimental anti-angiogenic agent. 4. Palliative surgery and/or radiation treatment < 4 weeks prior to Randomization. 5. Exposure to any investigational agent within 30 days of Randomization. 6. History of other malignancies (except cured basal cell carcinoma, superficial bladder cancer or carcinoma in situ of the cervix) unless documented free of cancer for \geq3 years. 7. Laboratory values: Screening serum creatinine $>1.5\times$ upper limit of normal (ULN), alanine aminotransferase (ALT) $> 2.5\times$ULN, total bilirubin $>1.5\times$ULN, absolute neutrophil count (ANC) $<1,500/\text{mm}^3$, platelet concentration $<100,000/\text{mm}^3$, absolute lymphocyte count $<1000/\text{mm}^3$, hematocrit level $<27\%$ for females or $<30\%$ for males, serum albumin ≤ 2.5 g/dL, prothrombin time (PT)/ international normalized ratio (INR) $>1.5\times$ULN or $>3\times$ULN on anticoagulant with no evidence of active bleeding. 	

Name of Sponsor/Company: CytRx Corporation	
Protocol Number: ALDOXORUBICIN-P2-GBM-01	Phase of Development: 2
8. Evidence of central nervous system (CNS) hemorrhage Common Terminology Criteria for Adverse Events (CTCAE) \geq grade 2 on baseline magnetic resonance imaging (MRI). 9. Clinically evident congestive heart failure (CHF) > class II of the New York Heart Association (NYHA) guidelines (see Appendix D). 10. Current, serious, clinically significant cardiac arrhythmias, defined as the existence of an absolute arrhythmia or ventricular arrhythmias classified as Lown III, IV or V (Appendix G). 11. Baseline QTc >470 msec and/or previous history of QT prolongation. 12. History or signs of active coronary artery disease with or without angina pectoris. 13. Serious myocardial dysfunction defined as ultrasound-determined absolute left ventricular ejection fraction (LVEF) <45% of predicted institutional normal value. 14. Active, clinically significant serious infection requiring treatment with antibiotics, anti-virals, or anti-fungals. 15. History of HIV infection. 16. Major surgery, except diagnostic tumor biopsy, within 4 weeks prior to Randomization. 17. Any condition that might interfere with the subject's participation in the study or in the evaluation of the study results. 18. Any condition that is unstable and could jeopardize the subject's participation in the study.	
Number of Subjects: Up to 28 subjects will be enrolled (14 at each dose level) in 3-5 study centers in the US.	
Test Product, Dose and Mode of Administration: Lyophilized powder in vials that contain 200 mg of ALDOXORUBICIN reconstituted by adding a sterile solution of 50:50 ethanol:water, administration completed within 2 hours (of being reconstituted) as a 30 minute IV infusion in Lactated Ringer's solution. Total doses of either 350 mg/m ² (260 mg/m ² doxorubicin equivalent) or 250 mg/m ² (185 mg/m ² doxorubicin equivalents).	
Reference Therapy, Dose and Mode of Administration: None	
Criteria for Evaluation:	
Efficacy: The following efficacy variables will be evaluated as noted:	

 • PFS • OS • Objective tumor response (RANO Working Group Criteria [see Appendix F]) • PFS at 12 and 18 weeks and 6 months • SD rate at 12 weeks • Karnofsky Performance Status (see Appendix B) • Corticosteroid usage 	
Safety: The following safety variables will be assessed over the course of the study:	

 • AEs • Ability to remain on assigned treatment (tolerability) • Clinical and laboratory data including physical examinations, vital signs, weight, ECHO evaluations, ECG results and laboratory test results • Use of concomitant medications 	

Name of Sponsor/Company: CytRx Corporation	
Protocol Number: ALDOXORUBICIN-P2-GBM-01	Phase of Development: 2
Statistical Methods: In accordance with the intention-to-treat principle, all randomized subjects who enter active treatment and have had at least 1 dose of study medication and 1 post-dose efficacy measurement will be included in the primary statistical analyses.	
Efficacy: Tumor response by MRI will be monitored every 6 weeks until disease progression. For the estimation of PFS and OS a Kaplan-Meier analysis will be performed. The percentage of subjects with CRs or PRs, or SD will be evaluated every 6 weeks.	
Safety: The safety data will be summarized for all subjects. Total number of AEs leading to withdrawal and abnormal laboratory tests will be evaluated. AEs, ability to remain on assigned treatment (tolerability), and abnormal findings on physical examinations, vital signs, weight, ECG results, ECHO, laboratory test results, and use of concomitant medications, will be assessed to characterize the safety profile of the treatment regimen. Descriptive evaluation denoting the changes from baseline to the final assessment visit with respect to key laboratory parameters and vital signs will also be provided.	

APPENDIX A: Schedule of Treatment and Evaluations

	Screening -21 Days	Cycle 1	All Other Cycles	Every 6 Weeks ± 5 Days from Cycle 1-Day 1	End of Study or Early Termination	Follow- up ¹²
Signed Informed Consent	X					
Review Inclusion/Exclusion		X				
Medical History ¹	X					
Physical Examination	X	X	X		X	
Height (cm)	X					
Weight (kg)	X	X	X			
BSA Calculation ²		X	X			
Vital Signs ³	X	X	X		X	
Karnofsky Performance Status	X	X	X		X	
MRI scan / Tumor Assessments	X ⁴			X ⁸	X ^{8,13}	
ECG	X	X ¹⁵	X ¹⁵		X ¹³	
ECHO (with ejection fraction)	X		X ¹¹		X ¹¹	
CBC w/differential & platelets ⁵	X	X ¹⁴	X		X	
Serum Chemistries ^{5,6}	X	X ¹⁴	X		X	
Urinalysis ⁷	X				X	
Serum/Urine Pregnancy Test	X					
ALDOXORUBICIN Administration		X	X			
Concomitant Medications ⁹	X	X	X		X	
Adverse Events ¹⁰		X	X		X	
Telephone Follow-Up						X

NOTE: All assessments must be performed within 72 hours of each specified time parameter, except Cycle 1 (see Section 6 for details).

CLINICAL PROTOCOL

TITLE: An Open-Label Pilot Phase 2 Study to Investigate the Preliminary Efficacy and Safety of Aldoxorubicin in Subjects with Unresectable Glioblastoma Whose Tumors Have Progressed Following Prior Treatment with Surgery, Radiation and Temozolomide

PROTOCOL NUMBER: ALDOXORUBICIN-P2-GBM-01

STUDY DRUG: Aldoxorubicin

IND NUMBER: 119437

SPONSOR: CytRx Corporation
[name]
[name]
[contact]
[contact]

SAFETY [contact]

SAFETY [contact]

ORIGINAL PROTOCOL: August 9, 2013

AMENDMENT 1: November 12, 2013

AMENDMENT 2: February 4, 2014

AMENDMENT 3: September 10, 2014

AMENDMENT 4: January 14, 2015

CONFIDENTIAL

The information contained in this document is confidential and the proprietary property of CytRx Corporation. Any unauthorized use or disclosure of such information without the prior written authorization of CytRx Corporation is prohibited.

SYNOPSIS

Name of Sponsor/Company: CytRx Corporation	
Protocol Number: ALDOXORUBICIN-P2-GBM-01	Phase of Development: 2
Title of the Protocol: An Open-Label Pilot Phase 2 Study to Investigate the Preliminary Efficacy and Safety of Aldoxorubicin in Subjects with Unresectable Glioblastoma Whose Tumors Have Progressed Following Prior Treatment with Surgery, Radiation and Temozolomide	
Primary Objectives: The primary objective of this study is to determine the preliminary efficacy of administration of ALDOXORUBICIN to subjects with unresectable glioblastoma (GBM) whose tumors have progressed following prior treatment with surgery, radiation and temozolomide, as measured by PFS according to the Response Assessment in Neuro-Oncology (RANO) Working Group Criteria (see Appendix F) and OS.	
Secondary Objectives: The secondary objectives of this study are to evaluate the safety of ALDOXORUBICIN in this population assessed by the frequency and severity of adverse events (AEs), abnormal findings on physical examination, laboratory tests, vital signs, echocardiogram (ECHO) evaluations, electrocardiogram (ECG) results, weight, and the change in performance status as measured by the Karnofsky Performance Scale.	
Study Rationale and Significance: ALDOXORUBICIN is a novel prodrug that binds covalently to albumin in the circulation. The drug is accumulated in tumors and doxorubicin is released in the tumor by cleaving the acid labile linker (EMCH) in the low pH tumor environment. This carrier-linked prodrug has demonstrated enhanced anti-tumor activity with reduced toxicity in several murine models when compared with free doxorubicin. Patients with unresectable GBM who have failed prior surgery, radiation and chemotherapy with temozolomide regimens and bevacizumab have an extremely poor prognosis with progression-free survival (PFS) of around 8 weeks and median overall survival (OS) of approximately 8-16 weeks, depending on whether salvage therapy is administered. Recently, we have demonstrated in an orthotopic xenograft model of GBM in mice that ALDOXORUBICIN significantly retards the growth of the tumor and doubles the survival of animals when compared to treatment with either saline or doxorubicin. We have also shown that this molecule collects inside the tumor and not in normal brain parenchyma. Doxorubicin does not penetrate into either the tumor or the brain. Thus, ALDOXORUBICIN may be able to effectively treat patients with advanced GBM that have progressed after standard therapies.	

Name of Sponsor/Company: CytRx Corporation	
Protocol Number: ALDOXORUBICIN-P2-GBM-01	Phase of Development: 2

Study Design and Methodology: This is a phase 2 open-label, pilot study evaluating the preliminary efficacy and safety of ALDOXORUBICIN administered at either 350 mg/m² (260 mg/m² doxorubicin equivalent) or 250 mg/m² (185 mg/m² doxorubicin equivalent) intravenously on Day 1, every 21 days until evidence of tumor progression, unacceptable toxicity or withdrawal of consent. Subjects will be randomly assigned to either dose of ALDOXORUBICIN. G-CSF (Neupogen or Neulasta) should be administered as primary prophylaxis to all subjects according to the ASCO Guidelines (see Appendix E). Note: ALDOXORUBICIN, at higher doses, has been associated with >20% incidence of grade 3 or 4 neutropenia. Therefore, the administration of G-CSF should occur even during Cycle 1 for subjects receiving the 350 mg/m² dose of ALDOXORUBICIN.
 
Tumor response (complete response [CR], partial response [PR] and stable disease [SD]) will be monitored at Screening, then every 6 weeks (±5 days) using the RANO Working Group Criteria (see Appendix F), and treatment will continue every 21 days until tumor progression is observed, unacceptable toxicity occurs, or consent is withdrawn. Median PFS, PFS at 12 and 18 weeks, and 6 months, SD rate at 12 weeks, and OS will be monitored as other primary objectives. Subjects will visit the study site every 21 days for their IV infusions, at which time safety monitoring, including AEs, a directed physical examination, laboratory evaluations (serum chemistry and complete blood count [CBC]), vital signs, weight measurements, Karnofsky Performance Status (see Appendix B), documentation of corticosteroid usage and ECGs will be performed. All subjects will have blood drawn for serum electrolytes to evaluate the anion gap prior to each drug administration. Cardiac function will also be followed periodically using ECHOs.
	

Name of Sponsor/Company: CytRx Corporation	
Protocol Number: ALDOXORUBICIN-P2-GBM-01	Phase of Development: 2

Study Population and Main Criteria for Inclusion/Exclusion:
 
Inclusion Criteria: Subjects must meet the following criteria to be included in the study:
 
 1. Age \geq18 years of age; male or female. 2. Histologically or cytologically confirmed unresectable GBM. Subjects with recurrent disease whose prior pathology demonstrated GBM will not need to be re-biopsied. Subjects with prior low-grade glioma or anaplastic glioma are eligible if histological assessment demonstrates transformation into GBM. 3. Cancer progression after treatment with the following: surgery, radiation therapy and temozolomide with no other therapy prior to tumor recurrence. 
 a. Radiographic progression by RANO Working Group Criteria (see Appendix F) will be confirmed by Imaging Endpoints, a central imaging vendor; or b. Confirmation by tumor biopsy if conducted within 4 weeks of Randomization. 4. An interval of at least 12 weeks after last dose of radiation and temozolomide is required, unless cancer progression is proven by diagnostic tumor biopsy. If temozolomide is being used in a maintenance phase, there must be a 28-day washout period prior to Randomization. 5. Stable or decreasing dose of corticosteroids for at least 7 days prior to Randomization. 6. Capable of providing informed consent and complying with trial procedures. 7. Karnofsky Performance Status (see Appendix B) \geq70. 8. Life expectancy \geq8 weeks. 9. Measurable tumor lesions according to RANO Working Group Criteria (see Appendix F). 
 a. In the case that there is "non-measurable" disease due to a radical surgical resection prior to screening, the subject may still qualify if Inclusion #3(b) is met. 10. Women must not be able to become pregnant (e.g. post-menopausal for at least 1 year, surgically sterile, or practicing adequate birth control methods) for the duration of the study. (Adequate contraception includes: oral contraception, implanted contraception, intrauterine device implanted for at least 3 months, or barrier method in conjunction with spermicide.) 11. Women of child bearing potential must have a negative serum or urine pregnancy test at the Screening Visit and be non-lactating. 12. Geographic accessibility to the site, i.e. the ability to come to the study site for each scheduled appointment and evaluation. 
Exclusion Criteria: Subjects meeting the following criteria will not be enrolled:
 
 1. Prior exposure to an anthracycline. 2. Any therapeutic regimen for treatment of recurrent tumor after first line treatment with surgery, radiation and temozolomide. 3. Prior treatment with bevacizumab or an experimental anti-angiogenic agent. 4. Palliative surgery and/or radiation treatment < 4 weeks prior to Randomization. 5. Exposure to any investigational agent within 30 days of Randomization. 6. History of other malignancies (except cured basal cell carcinoma, superficial bladder cancer or carcinoma in situ of the cervix) unless documented free of cancer for \geq3 years. 7. Laboratory values: Screening serum creatinine $>1.5\times$ upper limit of normal (ULN), alanine aminotransferase (ALT) $> 2.5\times$ULN, total bilirubin $>1.5\times$ULN, absolute neutrophil count (ANC) $<1,500/mm^3$, platelet concentration $<100,000/mm^3$, absolute lymphocyte count $<1000/mm^3$, hematocrit level $<27\%$ for females or $<30\%$ for males, serum albumin ≤ 2.5 g/dL, prothrombin time (PT)/ international normalized ratio (INR) $>1.5\times$ULN or $>3\times$ULN on anticoagulant with no evidence of active bleeding. 	

Name of Sponsor/Company: CytRx Corporation	
Protocol Number: ALDOXORUBICIN-P2-GBM-01	Phase of Development: 2

8. Anion gap > 16 meq/L or arterial blood pH < 7.30.
 
9. Evidence of central nervous system (CNS) hemorrhage Common Terminology Criteria for Adverse Events (CTCAE) ≥ grade 2 on baseline magnetic resonance imaging (MRI).
 
10. Clinically evident congestive heart failure (CHF) > class II of the New York Heart Association (NYHA) guidelines (see Appendix D).
 
11. Current, serious, clinically significant cardiac arrhythmias, defined as the existence of an absolute arrhythmia or ventricular arrhythmias classified as Lown III, IV or V (Appendix G).
 
12. Baseline QTc >470 msec and/or previous history of QT prolongation.
 
13. History or signs of active coronary artery disease with or without angina pectoris.
 
14. Serious myocardial dysfunction defined as ultrasound-determined absolute left ventricular ejection fraction (LVEF) <45% of predicted institutional normal value.
 
15. Active, clinically significant serious infection requiring treatment with antibiotics, anti-virals, or anti-fungals.
 
16. History of HIV infection.
 
17. Major surgery, except diagnostic tumor biopsy, within 4 weeks prior to Randomization.
 
18. Any condition that might interfere with the subject's participation in the study or in the evaluation of the study results.
 
19. Any condition that is unstable and could jeopardize the subject's participation in the study.
	
Number of Subjects: Up to 28 subjects will be enrolled (14 at each dose level) in 3-5 study centers in the US.	
Test Product, Dose and Mode of Administration: Lyophilized powder in vials that contain 200 mg of ALDOXORUBICIN reconstituted by adding a sterile solution of 50:50 ethanol:water, administration completed within 2 hours (of being reconstituted) as a 30 minute IV infusion in Lactated Ringer's solution. Total doses of either 350 mg/m ² (260 mg/m ² doxorubicin equivalent) or 250 mg/m ² (185 mg/m ² doxorubicin equivalents).	
Reference Therapy, Dose and Mode of Administration: None	
Criteria for Evaluation:	
Efficacy: The following efficacy variables will be evaluated as noted:	

 • PFS • OS • Objective tumor response (RANO Working Group Criteria [see Appendix F]) • PFS at 12 and 18 weeks and 6 months • SD rate at 12 weeks • Pseudo progression events on DSC-MRI in subjects who undergo additional MRI sequence evaluation • Karnofsky Performance Status (see Appendix B) • Corticosteroid usage 	

Name of Sponsor/Company: CytRx Corporation	
Protocol Number: ALDOXORUBICIN-P2-GBM-01	Phase of Development: 2

Safety: The following safety variables will be assessed over the course of the study:
 
 • AEs • Ability to remain on assigned treatment (tolerability) • Clinical and laboratory data including physical examinations, vital signs, weight, ECHO evaluations, ECG results and laboratory test results • Use of concomitant medications 	

Statistical Methods: In accordance with the intention-to-treat principle, all randomized subjects who enter active treatment and have had at least 1 dose of study medication and 1 post-dose efficacy measurement will be included in the primary statistical analyses.
 
Efficacy: Tumor response by MRI will be monitored every 6 weeks (± 5 days) until disease progression. For the estimation of PFS and OS a Kaplan-Meier analysis will be performed. The percentage of subjects with CRs or PRs, or SD will be evaluated every 6 weeks.
 
Safety: The safety data will be summarized for all subjects. Total number of AEs leading to withdrawal and abnormal laboratory tests will be evaluated. AEs, ability to remain on assigned treatment (tolerability), and abnormal findings on physical examinations, vital signs, weight, ECG results, ECHO, laboratory test results, and use of concomitant medications, will be assessed to characterize the safety profile of the treatment regimen. Descriptive evaluation denoting the changes from baseline to the final assessment visit with respect to key laboratory parameters and vital signs will also be provided.
	

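### Does the post-bevacizumab prognosis quoted in the rationale distort the efficacy reading in a trial that excludes bevacizumab-treated patients?

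*Combined protocol and SAP*

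**What the plan says.** All references are to the Amendment 4 synopsis unless stated.

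- **Study Rationale and Significance.** Patients who failed surgery, radiation and "chemotherapy with temozolomide regimens and bevacizumab have an extremely poor prognosis with progression-free survival (PFS) of around 8 weeks", together with "median overall survival (OS) of approximately 8-16 weeks, depending on whether salvage therapy is administered".
- **Inclusion criterion 3.** "Cancer progression after treatment with the following: surgery, radiation therapy and temozolomide with no other therapy prior to tumor recurrence".
- **Exclusion criterion 2.** "Any therapeutic regimen for treatment of recurrent tumor after first line treatment with surgery, radiation and temozolomide".
- **Exclusion criterion 3.** "Prior treatment with bevacizumab or an experimental anti-angiogenic agent".
- **Study Design and Methodology.** "Subjects will be randomly assigned to either dose of ALDOXORUBICIN".
- **Reference Therapy.** "Reference Therapy, Dose and Mode of Administration: None".
- **Number of Subjects.** Up to 28, with 14 at each dose level. No error rate, power or target effect accompanies the number.
- **Statistical Methods, Efficacy.** "For the estimation of PFS and OS a Kaplan-Meier analysis will be performed". No reference value is named.

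The rationale sentence is the same in the August 2013 protocol and in Amendments 1 to 4. Every version excludes prior bevacizumab. The exclusion of any treatment for recurrence is absent in August 2013 and present from Amendment 1 onward.

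**The concern.** The primary objective is preliminary efficacy, measured by PFS and OS. Both randomized groups receive aldoxorubicin, so the trial can contrast two doses but cannot show from its own data what PFS or OS would have been without an active drug. A reader who wants that answer needs an outside figure, and the only PFS and OS figures in the supplied text belong to patients who could not have been enrolled.

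The enrolled patients are at an earlier line of treatment, and the entry criteria also require a Karnofsky score of at least 70 and a life expectancy of at least 8 weeks, which is the low end of the quoted median OS. It is reasonable to suspect that they would do better than the quoted figures even on an inactive drug. Set against 8 weeks for PFS or 8-16 weeks for OS, that better prognosis could be mistaken for drug effect.

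**Working it through.** **1. Populations side by side.** The rationale describes failure of surgery, radiation, temozolomide and bevacizumab. Inclusion 3 with exclusions 2 and 3 admits progression after surgery, radiation and temozolomide only, with no bevacizumab and nothing given for the recurrence. No eligible subject belongs to the quoted population. This part of the concern is correct.

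**2. Where the figures are used.** The 8-week and 8-16-week values occur only in the rationale. The sample size is not derived from them. The objectives do not mention them. Statistical Methods estimates PFS and OS by Kaplan-Meier and names no null, margin, success threshold or historical comparison. There is therefore no figure in the plan to reproduce. Deleting or replacing the rationale sentence would leave every estimate unchanged.

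**3. How large the effect could be under an invented rule.** Suppose activity were claimed when the lower 95% Kaplan-Meier limit of median PFS exceeds 8 weeks. This rule is an assumption, as are exponential PFS, no censoring and the inactive-drug medians m of 10, 12 and 16 weeks.

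Without censoring, the lower limit of the median exceeds 8 weeks exactly when the lower limit of S(8) exceeds 0.5. The largest event count by week 8 that still meets this is 8 of 28 (log-log limits) or 9 of 28 (plain limits), and 2 of 14 or 3 of 14. For 8 of 28, for example, S(8) = 1 - 8/28 = 0.714 with a log-log lower limit of 0.509; at 9 events that limit falls to 0.473.

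Events by week 8 follow Binomial(n, q) with q = 1 - 2^(-8/m). The probability of passing is P(events ≤ cut-off):

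| m (weeks) | q | n=28 log-log | n=28 plain | n=14 log-log | n=14 plain |
|---|---|---|---|---|---|
| 8 | 0.500 | 0.018 | 0.044 | 0.006 | 0.029 |
| 10 | 0.426 | 0.094 | 0.178 | 0.026 | 0.089 |
| 12 | 0.370 | 0.236 | 0.374 | 0.063 | 0.177 |
| 16 | 0.293 | 0.561 | 0.712 | 0.175 | 0.377 |

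Check of one cell: for n=14, log-log and m=8, (1 + 14 + 91)/2^14 = 106/16384 = 0.0065.

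OS against 16 weeks with an assumed 24-week median uses q = 1 - 2^(-16/24) = 0.370, the same as the 12-week PFS row: 0.236 (n=28) and 0.063 (n=14), log-log.

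**4. Sensitivity to the scan schedule.** Tumor assessments are every 6 weeks (±5 days). If progression is dated only at scans held exactly on schedule, no event is recorded between weeks 6 and 8, so the observed S(8) equals S(6) and q becomes 1 - 2^(-6/m). For n=28, log-log, the results are 0.136, 0.348, 0.561 and 0.828 for m = 8, 10, 12 and 16. A population that truly matches the 8-week figure now passes in about 14% of trials instead of 1.8%. That exceeds the 9.4% shown for a 10-week median under continuous dating, so the invented rule misbehaves under this schedule even when the populations agree.

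**The case for a change.** The strongest argument for a change is that the pilot exists to give an efficacy reading, that such a reading without a control needs an outside reference, and that a protocol should not frame it with a population it excludes. The sentence also survived four amendments while eligibility was narrowed, and the remedy would be a sentence or two.

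Most of this is factually right. The mismatch stands, the arithmetic stands, and a reader who compared the results with the quoted figures would be making a poor comparison. Three things limit what follows.

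- The comparison is the reader's own. The plan does not propose it, so a disclaimer would rule out something never planned.
- The supplied file holds only synopses and Appendix A schedules. The synopses refer to a Section 6 and to further appendices, so there is a protocol body that could hold a suitable reference. A condensed rationale without citations does not show that none exists.
- PFS and OS against history are not the only evidence. Objective response by RANO is listed, and it does not lean on a PFS reference in the same way. The randomized dose contrast is internal, though weak with 14 subjects per dose.

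The probabilities do not rescue the point. They rest on a rule and medians found nowhere in the documents. They vary with the interval type, which the plan does not state, and with whether the doses are pooled, which it does not say either.

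**Conclusion.** No change to the plan is needed. The rationale describes a later-line population than the one enrolled, which is an imprecision in background text. No sample size, endpoint, analysis or threshold depends on it, so the effect on any planned result is nil.

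The size of a possible misreading cannot be taken from the documents, because they give no PFS or OS for bevacizumab-naive patients at first recurrence. Under the assumptions above (log-log limits, continuous dating, inactive-drug medians of 10 to 16 weeks), it runs from about 3% to 18% of trials with 14 subjects and from about 9% to 56% with 28. That measures an informal comparison someone might make later, not an error rate of this plan.

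An analyst reporting the trial would give Kaplan-Meier estimates with intervals and, if putting them in context, would choose a historical series that matches the eligibility criteria and has a similar scan interval. That is ordinary practice, and the present text does not prevent it. The conclusion would differ if the protocol body used 8 weeks, or 8-16 weeks, as a formal null or success criterion; nothing in the supplied text suggests that it does.
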